### 13.6.3 Misuse or abuse

The terms misuse and abuse are similar in that they both represent the intentional use of a drug in a way other than intended.

Misuse refers to situations where the IMP is intentionally and inappropriately used for therapeutic purposes not in accordance with the protocol.

Abuse refers to intentional use of an IMP for what could be considered desirable non-therapeutic effects (e.g. sedative, stimulant, euphoric effects).

Misuse and abuse must be recorded on the other event involving IMP form in the eCRF. In addition, any clinical consequences of misuse or abuse must be recorded as separate AEs on the AE form. If the AE originating from the misuse or abuse qualifies as an SAE, expedited reporting is required (Section 13.4).

#### 13.6.4 Aggravation of condition

Any clinically significant aggravation/exacerbation/worsening of any medical condition(s) (including the trial disease), compared to screening, must be reported as an (S)AE in accordance with Sections 13.3 and 13.4.

As CHE is a fluctuating disease, consider to only report an AE if aggravation/exacerbation exceeds normal disease fluctuation or if lesions appear in an area which is normally not affected by CHE.

#### 13.7 Follow-up for final outcome of adverse events

During the trial, the investigator should follow up for final outcome on all AEs (including SAEs). Once a subject leaves the clinical trial, the investigator should follow up on the outcome of all non-serious AEs classified as possibly or probably related to the IMP for 14 days after end of treatment, or until the final outcome is determined, whichever comes first. Non-serious AEs classified as not related to the IMP do not need to be followed up for the final outcome.

All SAEs must be followed up until a final outcome has been established, that is, the follow-up may continue beyond the end of the clinical trial. For SAEs which have stabilised and from which the subject cannot be expected to recover during the trial or the safety follow-up periods, e.g. chronic or stabilised conditions, the final outcome at the investigator's discretion should be reported as 'recovering/resolving' or 'not recovered/not resolved'. In addition, a statement detailing why the subject cannot be expected to recover during the trial, e.g. that the SAE has stabilised or is chronic, should be added to the narrative description of the SAE on the SAE form.

Any pregnancy occurring during the trial will be followed up as described in Section 13.5.1.

#### 13.8 Handling of an urgent safety measure

An urgent safety measure is a measure taken to implement an action/protocol deviation under an emergency. This is defined as “...*the occurrence of any new event relating to the conduct of the trial or the development of the investigational medicinal product where that new event is likely to affect the safety of the subjects, the sponsor and the investigator shall take appropriate urgent safety measures to protect the subjects against any immediate hazard.*” (40).

If the investigator becomes aware of information that requires an immediate change in a clinical trial procedure or a temporary halt of the clinical trial to protect clinical trial subjects

THIS DOCUMENT CONTAINS CONFIDENTIAL INFORMATION AND MUST NOT BE COPIED OR MADE AVAILABLE TO ANY THIRD PARTY WITHOUT THE PRIOR WRITTEN CONSENT OF THE LEO PHARMA GROUP

from any immediate hazard to their health and safety, the investigator can do so without prior approval from LEO Pharma, regulatory authorities, or IRBs/IECs.

The investigator must immediately inform LEO Pharma – by contacting the clinical project manager or medical expert – of this change in a clinical trial procedure or of the temporary halt; the investigator will provide full details of the information and the decision-making process leading to the implementation of the urgent safety measure.

LEO Pharma must act immediately upon receipt of the urgent safety measure notification in accordance with internal procedures and local legislation.

THIS DOCUMENT CONTAINS CONFIDENTIAL INFORMATION AND MUST NOT BE COPIED OR MADE AVAILABLE TO ANY THIRD PARTY WITHOUT THE PRIOR WRITTEN CONSENT OF THE LEO PHARMA GROUP

## 14 Statistical methods

Endpoints will be analyzed using 2 different statistical approaches: the Bayesian and the Frequentist approach.

### 14.1 Sample size

92 subjects will be randomised 3:1 to delgocitinib cream 20 mg/g or cream vehicle.

Based on response rates from the phase 2b dose-ranging trial in adults (LP0133-1273), a one-sided significance level at 2.5% and a sample size of 92 subjects will provide at least 80% power for detecting a treatment difference in the primary endpoint assuming an IGA-CHE TS response at Week 16 of 40.2% for delgocitinib cream 20 mg/g and 10.5% for cream vehicle.

When the response rates from LP0133-1401 and LP0133-1402 are included in the sample size calculation, this will result in a power which is lower than first anticipated.

The power obtained when using the Bayesian approach on a sample size of 92 subjects is explained in Section [14.3.17](#).

### 14.2 Trial analysis sets

All screened subjects will be accounted for in the CTR.

All subjects randomised and exposed to IMP will be included in the full analysis set and will be analysed for efficacy. Exclusions from the full analysis set can be considered in special cases as described in ICH E9, Section 5.2.1., Full Analysis Set. If it is decided to exclude a randomised subject exposed to IMP from the full analysis set, a justification addressing ICH E9 will be given.

A safety analysis set will be defined as all subjects exposed to IMP.

The decisions regarding inclusion/exclusion of subjects or subject data from the trial analysis sets will be documented in the analysis set definition document before breaking the randomisation code.

### 14.3 Statistical analysis

#### 14.3.1 Disposition of subjects

The reasons for permanent discontinuation of IMP or withdrawal from trial will be presented for all randomised subjects by last visit attended and by treatment group.

THIS DOCUMENT CONTAINS CONFIDENTIAL INFORMATION AND MUST NOT BE COPIED OR MADE AVAILABLE TO ANY THIRD PARTY WITHOUT THE PRIOR WRITTEN CONSENT OF THE LEO PHARMA GROUP

An overall summary of subject disposition will be presented for all randomised subjects. The disposition summary will include information on the number of randomised, exposed, included in the full analysis set, permanently discontinuing IMP, and not completing the trial by treatment group and overall.

#### **14.3.2 Demographics and other baseline characteristics**

Descriptive statistics of demographics and other baseline characteristics will be presented for all randomised subjects and by treatment group. Presentations of age, sex, ethnicity, race, and baseline IGA-CHE by treatment will also be given.

Other baseline characteristics include height, weight, body mass index, region, country, Fitzpatrick skin type, CHE history, CHE treatment history, past and current medical history, and prior and concomitant medication. In addition, the baseline assessment for the primary and key secondary endpoints will be presented.

#### **14.3.3 Exposure and treatment compliance**

The duration of exposure to treatment in a specific visit interval will be calculated as the number of days from date of first application of IMP in that period to the date of last application of IMP in that period, both days included.

Exposure to treatment will be presented for the safety analysis set as days of exposure per treatment group.

The average weekly and total amount of IMP used will be presented for the safety analysis set by treatment group for each visit interval and for the total treatment period.

Treatment compliance will be presented for the safety analysis set per treatment group.

#### **14.3.4 Testing strategy and establishing confirmatory evidence using Bayesian analysis**

The Bayesian analyses of the primary estimand for the primary and key secondary endpoints are considered the confirmatory evidence for the trial. The treatment effect (defined as proportion of responders for delgocitinib cream 20 mg/g minus the proportion of responders for cream vehicle) for all the binary confirmatory endpoints will be evaluated based on the calculated difference of posterior distributions for delgocitinib cream 20 mg/g and cream vehicle. Delgocitinib cream 20 mg/g is considered superior to cream vehicle if the 2.5% percentile of the posterior distribution of the treatment difference is  $\geq 0$ .

[figure not shown]

Hierarchical evaluation, which is applied for the Bayesian analyses, will be used to control the overall type I error at a nominal one sided 2.5% level. This is built on the principle that the IGA-CHE TS superiority at Week 16 will have to be established before sequential testing for additional benefits (key secondary endpoints) related to efficacy.

If superiority is claimed for the primary endpoint, then evaluation of the next endpoints will be done in a fixed sequential order as specified in [Panel 16](#). This process will be repeated until no further tests are significant.

Only analyses based on the Bayesian approach will be part of the testing hierarchy.

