#### 14.3.17 Description of the Bayesian analyses and design characteristics

The design characteristics is based on 92 randomised subjects (69 in the delgocitinib cream 20 mg/g group and 23 in the cream vehicle group).

For each endpoint, the choice of the between-trial heterogeneity parameter ( $\tau$ ) and the weight on the non-informative part of the prior is described. In addition, the degree of borrowing is described by the ESS and finally, the influence of the type I error and power investigated.

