#### 14.3.17.2 Evaluation of design characteristics (type I error, power and bias) for the Bayesian analysis of the primary endpoint

The between-trial heterogeneity for the primary endpoint IGA-CHE TS is set to  $\tau = 0.5$ , the weight on the non-informative part of the prior is set to 0.2 (20%).

This ensures a type I error <5% for efficacy rates <10% (average observed efficacy rates for cream vehicle was 8.4% in the adult trials LP0133-1401 and LP0133-1402) and a high power (>75%) for efficacy levels above observed efficacy levels (average difference in adult trials is 15.9%).

In the following sections, the selection of the parameters for the primary endpoint IGA-CHE TS are justified and discussed.

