**The level of type I error and power as a function of the difference in proportion of IGA-CHE TS at Week 16**

[figure not shown]
The influence of  $\tau$  and weight on the type I error and the power is shown in [Panel 31](#). Overall, the type I error decreases as  $\tau$  and weight increase, and it peaks just above the average observed response rate in the historical data. The power is increasing with increasing difference and lower  $\tau$  and weight.

The average response rate for cream vehicle on IGA-CHE TS at Week 16 in the adult trials (LP0133-1401 and LP0133-1402) is 8.4% ([Panel 21](#)), corresponding to a type-I error of <5% ([Panel 31](#)). The average treatment effect is 15.9% ([Panel 21](#)), corresponding to a power of >75% ([Panel 31](#)).

THIS DOCUMENT CONTAINS CONFIDENTIAL INFORMATION AND MUST NOT BE COPIED OR MADE AVAILABLE TO ANY THIRD PARTY WITHOUT THE PRIOR WRITTEN CONSENT OF THE LEO PHARMA GROUP

**Panel 31: The level of type I error and power as a function of the difference in proportion of IGA-CHE TS responders at Week 16, split on the level of  $\tau$  and the weight put on the non-informative part of the robust prior**

**Abbreviations:** IGA-CHE = Investigator's Global Assessment for chronic hand eczema®. IGA-CHE TS = IGA-CHE treatment success, i.e. an IGA-CHE score of 0 (clear) or 1 (almost clear) with a  $\geq 2$ -step improvement from baseline.

**Notes:** tau =  $\tau$ , the between-trial heterogeneity. Weigh represents the non-informative part of the prior. The blue circles mark the anticipated type I error and power with the predefined selections of  $\tau = 0.5$  and weight = 0.2, for the average response rates for cream vehicle and delgocitinib cream 20 mg/g in the adult trials.

THIS DOCUMENT CONTAINS CONFIDENTIAL INFORMATION AND MUST NOT BE COPIED OR MADE AVAILABLE TO ANY THIRD PARTY WITHOUT THE PRIOR WRITTEN CONSENT OF THE LEO PHARMA GROUP

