### Conclusion on hypothetical examples

The hypothetical examples illustrate that if the treatment difference between delgocitinib cream 20 mg/g and cream vehicle in trial LP0133-1426 is similar to the treatment difference in the adult trials (example 1), then the Bayesian analysis gives a confirmatory result for IGA-CHE TS. If the treatment difference is markedly lower in trial LP0133-1426 than in adult trials (example 2), then the Bayesian analysis will not confirm a difference between delgocitinib cream 20 mg/g and cream vehicle in IGA-CHE TS.

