**Panel 10: Beta mix components for the prior distribution for IGA-CHE vehicle responders from LP0133-1401 and LP0133-1402**

	Component 1	Component 2	Component 3	Component 4	Robust
W	0.42	0.28	0.06	0.04	0.20
A	16.36	3.44	5.86	1.16	1.00
B	180.23	39.78	35.60	5.07	1.00

**Note:** Not rounded data can be found in /leo/clinical/lp0133/1426/stat/sap/rob\_viga.xpt.

**Panel 11: Beta mix components for the prior distribution for IGA-CHE delgocitinib 20 mg/g responders from LP0133-1401 and LP0133-1402**

	Component 1	Component 2	Component 3	Component 4	Robust
W	0.38	0.16	0.13	0.12	0.20
A	21.30	6.35	1.55	14.15	1.00
B	66.59	30.83	3.26	27.17	1.00

**Note:** Not rounded data can be found in /leo/clinical/lp0133/1426/stat/sap/rob\_diga.xpt.

THIS DOCUMENT CONTAINS CONFIDENTIAL INFORMATION AND MUST NOT BE COPIED OR MADE AVAILABLE TO ANY THIRD PARTY WITHOUT THE PRIOR WRITTEN CONSENT OF THE LEO PHARMA GROUP

Once the trial is unblinded the posterior distributions for the proportion of responders for vehicle and delgocitinib 20 mg/g for IGA-CHE given the robust mixture priors can be calculated with the 'postmix' function in the statistical package 'RBesT'.

The conclusion on treatment effect will be based on the calculated difference (based on 1.000.000 samples) in the posterior distributions. A statistically significant treatment effect is concluded if the probability that the difference (delgocitinib cream 20 mg/g minus cream vehicle) is larger than zero, is larger than 0.975. That is if  $P(\text{delgocitinib cream 20 mg/g} - \text{cream vehicle} > 0) > 0.975$ . The 95% credibility interval (generated as the 2.5% and 97.5% quantiles of the difference in posterior distributions) will be presented along with the mean and median.

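### The stated one-sided 2.5% type I error control does not hold for the Bayesian rule: the error reaches 15.7% for IGA-CHE TS and 17.6% to 24.6% per test for the key secondary endpoints

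*Protocol*

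**What the plan says.** Only the Bayesian analyses enter the testing hierarchy, and they are the trial's confirmatory evidence. The synopsis, Protocol 14.3.4 and SAP 2.1 say that the hierarchy "will be used to control the overall type I error at a nominal one sided 2.5% level". For each endpoint, superiority is declared when the posterior probability that the difference "is larger than zero, is larger than 0.975" (SAP 5.5.1.7).

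Protocol 14.3.17 gives the operating characteristics for "92 randomised subjects (69 in the delgocitinib cream 20 mg/g group and 23 in the cream vehicle group". For IGA-CHE TS, with τ = 0.5 and a non-informative weight of 0.2, section 14.3.17.2 says: "This ensures a type I error <5% for efficacy rates <10" per cent, with power above 75%. For each key secondary endpoint, section 14.3.17.3 gives a type I error below 5% at the adult vehicle rate and power above 80%. On the shape of the IGA-CHE TS error curve, the text says only that "it peaks just above the average observed response rate in the historical data". The text gives no maximum for any endpoint.

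**The concern.** A fixed sequence adds no inflation, but it cannot repair a component test that exceeds its level. If IGA-CHE TS has no true effect, the overall error is simply the error of that first test. A statement of 2.5% overall control and a statement of less than 5% over a limited range cannot both describe the same rule.

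The mechanism is borrowing in each arm separately. The vehicle estimate is pulled towards adult vehicle and the delgocitinib estimate towards adult delgocitinib, so a difference can be added when the adolescent rates are equal. All five confirmatory claims would be read against an error rate that the design does not have.

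**Working it through.** **Inputs.** 69 delgocitinib and 23 vehicle subjects (Protocol 14.3.17); threshold 0.975 (SAP 5.5.1.7); robust beta-mixture priors from SAP Panels 10–11 (IGA-CHE TS), 13–14 (HECSI-90), 16–17 (itch), 19–20 (pain) and 22–23 (HESD), with the two-decimal weights renormalised to sum to 1; adult rates from Protocol Panels 21, 36, 39, 42 and 45.

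**Method (exact, no simulation).** For r responders out of n, prior component k becomes Beta(a_k + r, b_k + n − r), with weight proportional to w_k · B(a_k + r, b_k + n − r) / B(a_k, b_k). For each of the 70 × 24 outcomes (x on delgocitinib, y on vehicle), compute P(p_D > p_V | x, y) by numerical integration. Let S be the set of outcomes where it exceeds 0.975. Then

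- type I error at common rate p = Σ over S of Bin(x; 69, p) · Bin(y; 23, p);
- power = Σ over S of Bin(x; 69, p_D) · Bin(y; 23, p_V).

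**The plan's own figures reproduce.** IGA-CHE TS at 24.3% against 8.4% has power 79.0% (stated above 75%) and error 2.8% at 8.4% (stated below 5%). Example 1 (22/69 against 3/23) gives 0.994, significant. Example 2 (22/69 against 7/23) gives 0.627, not significant. For the key secondary endpoints see the last two columns of the second table (stated: error below 5%, power above 80%).

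**IGA-CHE TS, equal true rates in both arms:**

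| Common rate | Where the rate comes from | Type I error |
|---|---|---|
| 8.4% | adult vehicle, phase 3 | 2.8% |
| 10% | limit of the stated range | 5.2% |
| 10.5% | phase 2b vehicle, moderate to severe | 6.0% |
| 13% | Example 1 vehicle, 3/23 | 10.6% |
| 15% | | 13.6% |
| 18.8% | maximum | 15.7% |
| 24.3% | adult delgocitinib, phase 3 | 13.0% |
| 30% | | 9.0% |

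The error is above 5% from about 10% to 38.5%. At a common rate of 18.8% the expected posterior mean difference is +5.5 points although the true difference is 0. The coarser priors printed in Protocol Panels 25 and 29 give the same maximum (15.7%), so rounding does not drive it.

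**Key secondary endpoints, per test, full 69/23:**

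| Endpoint | Maximum error | at common rate | Error at adult vehicle rate | Power |
|---|---|---|---|---|
| HECSI-90 | 24.6% | about 22% | 3.6% | 88.6% |
| HESD itch | 22.5% | 36% | 2.5% | 92.8% |
| HESD | 18.2% | 36% | 3.1% | 87.2% |
| HESD pain | 17.6% | 39.5% | 3.5% | 88.6% |

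The HESD endpoints use only subjects with a baseline score of at least 4, so their denominators will be smaller. Assuming 21/63 or 18/55 (vehicle/delgocitinib), the three HESD maxima stay between 17.8% and 22.6%.

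**Decision boundary, IGA-CHE TS.** Minimum delgocitinib responders out of 69 for a superiority claim:

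| Vehicle responders out of 23 | 0 | 1 | 2 | 3 | 4 | 5 | 6 | 7 |
|---|---|---|---|---|---|---|---|---|
| Minimum on delgocitinib | 9 | 11 | 12 | 16 | 22 | 28 | 33 | 37 |

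For example, 12/69 against 2/23 (17.4% against 8.7%) gives 0.977 and is declared superior; the one-sided Fisher p-value for the same table is 0.26.

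**The case against.** **Borrowing trades type I error for power, and the plan partly says so.** It uses the word nominal and reports an error below 5%. That is fair. With no borrowing (weight 1) the maximum is 2.6% but power falls to 35%. Holding the IGA-CHE TS maximum at 2.5% under these priors would need a threshold between 0.995 (maximum 3.6%, power 48%) and 0.9975 (maximum 2.0%, power 36%). This defends the design. It does not defend the sentence saying that 2.5% is controlled.

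**The maxima lie at less likely rates.** The informative part of the SAP vehicle prior puts about 12% probability above 13% and 4% above 18.8%; averaging the equal-rate error over that prior gives 4.0%. This should be reported beside the maximum. It is still above 2.5%, and two of the elevated rates (10.5% and 13%) come from the protocol itself.

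**The curves may be plotted.** Panels 31, 37, 40, 43 and 46 plot type I error, but the figures were not available for this review. They may show the full range. The text still states 2.5% and gives no maximum.

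**Other analyses would expose a claim driven by borrowing.** SAP 5.5.1.9 varies τ and the weight, including full weight on the non-informative part, and frequentist and treatment-by-trial analyses are planned. These show how far a result depends on the prior; they do not give the error rate of the rule.

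**Stronger readings that the documents do not support.**
- A reader might infer that the sentence on where the error peaks is false. It names no arm. The midpoint of the two adult rates is (8.4 + 24.3)/2 = 16.4%, so the sentence is ambiguous.
- A reader might infer that the worst case is adolescents responding better than adults in both arms. The maximum lies between the adult rates, and the IGA-CHE TS error is falling by 24.3%.
- A reader might take 12/69 against 2/23 as refuting the statement that "then the Bayesian analysis will not confirm a difference between delgocitinib cream 20 mg/g and cream vehicle in IGA-CHE TS". That statement is tied to Example 2 and a markedly lower difference. In this case vehicle matches adult vehicle, and the 8.7-point difference is near the 9.8 points (19.7% against 9.9%) seen in LP0133-1401.

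**Conclusion.** The 2.5% control statement is wrong as written and should be corrected before unblinding. The IGA-CHE TS error is already 2.8% at the adult vehicle rate and reaches 15.7% near 18.8%. If that endpoint is truly null, its error bounds the overall error. The key secondary maxima of 17.6% to 24.6% apply only when testing reaches that step. If IGA-CHE TS works at adult rates (power 79.0%), HECSI-90 is tested second and the endpoints are independent (both assumptions; the order is in a figure not available here), the HECSI-90 maximum becomes 0.246 × 0.790 = 19.4%.

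The results rest on the SAP's rounded priors, 69/23 and equal true rates in the two arms. They do not show that the Bayesian analysis is unusable or that false claims are several times likelier at all plausible rates. Near adult vehicle rates the errors are 2.5% to 3.6%, within the plan's own bound of 5%.

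**What to change.** 1. In the synopsis, Protocol 14.3.4 and SAP 2.1, replace the statement of 2.5% control. Give the achieved type I error for each confirmatory endpoint over the range of common response rates, with the maximum and its location in the text. Say that the key secondary figures are conditional on passing the earlier steps. The fixed sequence can stay as the rule for the order of claims.
2. In the type I error discussion under Protocol 14.3.17.2, say which average response rate the peak is compared with, and give the location and value of the peak.
3. Beside the two hypothetical examples, add the decision boundary, for instance that 2/23 on vehicle needs at least 12/69 on delgocitinib.

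The cost is wording and a less favourable stated error figure. No change to priors, threshold or sample size is needed. Raising the threshold to 0.98 is an optional trade-off: the IGA-CHE TS maximum would be 12.9% and power 75.2%, so it would not restore 2.5%.

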### Panel 16: Graphical display of the testing procedure for primary and secondary endpoints

\* From baseline in subjects with baseline  $\geq$  threshold of response

† Average score of 6 symptom items, i.e., itch, pain, cracking of the skin, redness, dryness, and flaking

**Abbreviations:** HECSI-90 = at least 90% improvement in HECSI score from baseline; HESD = Hand Eczema Symptom Diary®; IGA-CHE = Investigator's Global Assessment for chronic hand eczema®; IGA-CHE TS = IGA-CHE treatment success, i.e. an IGA-CHE score of 0 (clear) or 1 (almost clear) with a  $\geq 2$ -step improvement from baseline.

